3.6.2 Plasma Pharmacokinetic Parameters

The plasma PK of ISIS 757456 (as total full-length oligonucleotides) will be assessed following the first SC dose. Non-compartmental PK analysis of ISIS 757456 (total full-length oligonucleotides) will be carried out on each individual subject data set using Phoenix WinNonlin version 8.0 or higher (Pharsight Corporation, Mountain View, CA). For calculation of PK parameters, all BLQ values will be set to zero. The plasma PK parameters for ISIS 757456eq. will be calculated based on actual sampling times. The plasma PK parameters to be calculated or determined (when applicable) are listed in Table 1. Other plasma PK parameters, as appropriate, may be determined or calculated at the discretion of the PK scientist.

Table 1 Plasma Pharmacokinetic Parameters to be Calculated or Determined

Parameter	Definition/Method	Multiple-dose
		D1
C_{max}	Maximum observed concentration	X
T_{max}	Observed time at which C_{max} occurs	X
T_{last}	Time of last measurable (positive) concentration	X
AUC_{0-t}	Partial AUC: Area under the concentration-time curve from time zero to time t (e.g., t may be 24, 48, 72, or 168 hrs, as applicable), calculated using linear-up log-down method	X
CL_{0-t}/F	Partial clearance divided by F (fraction of the dose absorbed) determined by $Dose/AUC_{0-t}$	X

Note: X designates parameters to be calculated or determined assuming sufficient data

Plasma pharmacokinetic parameters will be summarized using descriptive statistics (n, mean, SD, %CV, geometric mean, geometric %CV, median, minimum, and maximum) by treatment group, dose cohort, nominal dose, and day.

3.6.3 Pharmacokinetic/Pharmacodynamic Exposure-Response Analysis

Exposure-response correlations maybe explored graphically between plasma exposure (AUC, C_{max} , C_{min} , as appropriate), and selected PD measures (e.g. serum AGT level), other relevant biomarkers (such as plasma renin activity, angiotensin II, etc) and relevant clinical endpoints (such as in-clinic systolic blood pressure). In addition, the relationship between serum AGT level with plasma concentrations (C_{max} , C_{min} , as appropriate) of ISIS 757456 eq. may be further evaluated with an inhibitory effect E_{max} model.

Population PK and PKPD analysis may be performed using the PK and PD data from this Study, and/or combined with other ISIS 757456 clinical PK/PD data from any previous and future studies in the development timeline.

3.6.4 Immunogenicity (IM) Analysis

The samples for immunogenicity are not planned to be analyzed.

3.7 Safety Analyses

The safety analysis will be conducted on the Safety Set.

3.7.1 Exposure

Treatment duration and amount of Study Drug (ISIS 757456 or placebo) received will be summarized by treatment group. The treatment duration for each subject is defined as last dose date - first dose date +1.

3.7.2 Adverse Events

The incidence of AEs will be summarized by Medical Dictionary for Regulatory Activities (MedDRA) version 21.1 preferred term and system organ class for:

- Any treatment emergent adverse events
- Related treatment emergent adverse events. Related is defined as “Related”, “Possible”, or missing relationship to study drug
- Any treatment emergent adverse events by severity. At each level of subject summarization, a subject is classified according to the highest severity if the subject reported one or more events. Adverse events with missing severity will be categorized as “Missing” for this summary
- Serious treatment emergent adverse events

SAEs and TEAEs that lead to study discontinuation or investigational drug discontinuation will be listed separately. Non-treatment emergent adverse event will be flagged in the data listing.

An adverse event will be regarded as treatment emergent if it is present prior to receiving the first dose of study drug or placebo and subsequently worsened, or is not present prior to receiving the first dose of study drug or placebo but subsequently appeared.

If there is no “Formlink” link, and the AE (start date/time) occurs after the subject’s first dosing date/time, then the AE is treatment-emergent. Otherwise, if the AE (start date/time) occurs prior to the subject’s first dosing date/time, then the AE is not treatment-emergent.

If there is a “Formlink” link between two AE records, then we compare them pairwise, and consider two cases, where we compare the AE severity (mild/moderate/severe) between the two records in the pair. We chronologically order the 2 records (by AE start date) and refer to the “first” and “second” AEs.

Case 1: The first AE record in the pair occurs before first dosing, and the second record occurs after dosing.

If the AE severity on the second record is worse than the severity on the first record, then only count the second AE as treatment-emergent. But, if the severity improves (second record severity is less severe than the first record severity), then neither record is counted as treatment-emergent.

Case 2: Both AE records in the pair occur after first dosing.

If the AE severity on the second record is worse than the severity on the first record, then count both records as treatment-emergent. But, if the severity improves, then only count the first record as treatment-emergent.

When counting the total number of treatment-emergent events, events linked together through change in severity will still be counted as separate events.

The most conservative approach will be used to determine if the event occurs after the treatment. For example, if the onset date or resolution date of an AE is prior to the first study treatment date, it will be considered to have occurred prior to the study period. If the onset or resolution date of an AE is a partial date with only month or year available or complete missing, then the event is assumed to be within the study period unless the year is prior to the year of the first study treatment date, or if in the same year, the month is prior to the month of the first study treatment date.

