9.4.3.5. Outcome of the Adverse Event

If the event is a non-serious AE, then the event's outcome is characterized by 1 of the following:

- **AE Persists:** Patient terminates from the trial and the AE continues
- **Recovered:** Patient recovered completely from the AE
- **Became Serious:** The event became serious (the date that the event became serious should be recorded as the Resolution Date of that AE and the Onset Date of the corresponding SAE)
- **Change in Severity (if applicable):** AE severity changed

If the event is an SAE, then the event's outcome is characterized by 1 of the following:

- **Ongoing:** SAE continuing
- **Persists (as non-serious AE):** Patient has not fully recovered but the event no longer meets serious criteria and should be captured as an AE on the non-serious AE eCRF (the SAE resolution date should be entered as the date of onset of that AE)
- **Recovered:** Patient recovered completely from the SAE (the date of recovery should be entered as the SAE resolution date)
- **Recovered with Sequelae:** The signs/symptoms of the reported SAE have improved but not completely resolved, and a new baseline for the subject is established since full recovery is not expected
- **Fatal:** Patient died (the date of death should be entered as the SAE resolution date)
- **Unknown:** The outcome of the reported SAE is not available, e.g., patient is lost to follow-up

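### SAP 3.7.2 judges linked adverse-event records pair by pair without asking whether the chain began before dosing, so a record can get two opposite verdicts and an event that never exceeds its pre-dose grade can be tabulated as treatment-emergent.

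*Combined protocol and SAP*

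**What the plan says.** SAP 3.7.2 (Adverse Events) opens with a general definition. An event is treatment-emergent "if it is present prior to receiving the first dose of study drug or placebo and subsequently worsened", or if it "is not present prior to receiving the first dose of study drug or placebo but subsequently appeared".

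It then gives an operational rule for records joined by a Formlink: "then we compare them pairwise, and consider two cases". The comparison uses three grades, "where we compare the AE severity (mild/moderate/severe) between the two records in the pair".

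- **Case 1** (first record before dosing, second after). If the second is worse, only the second counts. If it is milder, "then neither record is counted as treatment-emergent".
- **Case 2** (both records after dosing). If the second is worse, both count. If it is milder: "But, if the severity improves, then only count the first record as treatment-emergent".

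The section has no rule for chains of three or more records, no precedence when two pairs classify the same record differently, and no branch for equal grades. Classification by start date alone is reserved for records without a link. The section's remark about taking a conservative approach is illustrated only with onset and resolution dates, so it does not settle conflicts over severity.

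**The concern.** Both branches of Case 2 count the earlier record of a post-dose pair. That suits an event that first appeared after dosing. It does not suit a pair that continues a pre-dose event, yet Case 2 makes no exception for one.

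Such chains can arise. Adverse events are recorded from consent (protocol 9.4.1 and 9.4.2), and screening starts at Week -6. Antihypertensives stop two weeks before Study Day 1 (protocol 3.4.2). A change in severity is a recordable outcome with no limit on repeats (protocol 9.4.3.5).

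Incidence and severity of treatment-emergent events is a listed safety endpoint (protocol 1.2.3, SAP 1.3.3). If the rule yields two answers for one record, two programmers following the text could produce different tables. If it counts a relapse that only returns to the pre-dose grade, the tables include events that had not worsened from the state before treatment.

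**Working it through.** The plan states no figure here, so the check applies Cases 1 and 2 literally to every possible short chain.

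**Inputs.** Three grades, mild, moderate and severe (SAP 3.7.2). Record A is pre-dose; B and C are post-dose. The grade changes at each step. Links are A–B and B–C.

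**Number of chains.** 3 grades for A × 2 different grades for B × 2 different grades for C = 12.

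**Two-record events.** Wherever the grade changes, Cases 1 and 2 agree with the general definition. Equal grades fall in neither branch.

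**Where the cases conflict.** Case 1 excludes B whenever B is milder than A. Case 2 counts B whatever C is. So every chain with B milder than A gives B two verdicts. There are 3 such A–B combinations (moderate–mild, severe–mild, severe–moderate) × 2 grades for C = 6 chains:

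| A (pre-dose) | B | C | B by Case 1 | B by Case 2 | C by Case 2 | Exceeds pre-dose grade? |
|---|---|---|---|---|---|---|
| severe | moderate | mild | no | yes | no | no |
| moderate | mild | moderate | no | yes | yes | no |
| severe | mild | moderate | no | yes | yes | no |
| severe | mild | severe | no | yes | yes | no |
| severe | moderate | severe | no | yes | yes | no |
| moderate | mild | severe | no | yes | yes | yes |

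In the other 6 chains B is worse than A, and B counts under both cases.

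**The five chains that never exceed the pre-dose grade.**

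- Severe–moderate–mild is the only one of the 12 that purely improves. The event is treatment-emergent if a positive pair prevails and not if a negative pair prevails. The SAP does not say which.
- In the other four, C is worse than B, so Case 2 counts C. With adjacent links no other pair judges C, and the event is treatment-emergent under any precedence. Because SAP 3.7.2 classifies a subject by highest severity, severe–moderate–severe could enter the table as a severe event.

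**If A and C are also linked.** In three of those four, A and C have equal grades. Case 1 has no branch for that, so C still counts. In severe–mild–moderate, Case 1 now excludes C while Case 2 counts it, which adds a second conflict. Severe–moderate–mild is unchanged.

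**Scale.** About 30 subjects randomized 2:1 (protocol 3.1 and 3.3) gives 30 × 2/3 = 20 active and 30 × 1/3 = 10 placebo. One reclassified subject moves incidence by 100/20 = 5 points (active) or 100/10 = 10 points (placebo).

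**The case against.** **The definition names no reference grade.** In the four relapse chains the event does worsen between two post-dose records, so counting C could be called consistent with the definition. This stands in part: the conflict with the definition in those chains depends on judging worsening against the pre-dose state. It does not rescue the middle record. In all six chains B is milder than A, and the SAP still both excludes and counts it.

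**A stronger reading of Case 2.** A reader might infer that any pre-dose event with two post-dose records becomes treatment-emergent even if it only improves. The documents do not support that. The grade must also change between the two post-dose records. Only severe–moderate–mild purely improves, and there the SAP gives conflicting verdicts rather than a settled one. A three-record chain whose pre-dose grade is mild or moderate cannot show the problem by improvement alone.

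**Serious events.** A reader might also infer that an event turning serious at the same grade escapes classification. Protocol 9.4.3.5 does open a separate record: "the date that the event became serious should be recorded as the Resolution Date of that AE and the Onset Date of the corresponding SAE". But the SAP describes links through change in severity, and nothing shows that these records are Formlinked. If they are not, the start-date rule applies and an event that becomes serious after dosing is treatment-emergent. The claim cannot be made from the documents.

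**Frequency.** The documents give no rate for such chains. A reclassified record changes a row of the incidence table only if that subject has no other treatment-emergent event in the row. Non-emergent events are flagged in the listing, so the classification can be inspected. All of this limits the likely effect, but none of it tells a programmer which verdict to use.

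**Conclusion.** The point holds as a defect in a stated rule. Case 2 takes no account of a linked pre-dose record. As a result, 6 of the 12 three-record chains give opposite verdicts on the middle record with no precedence. Of those 6, 5 never exceed the pre-dose grade, and in 4 of the 5 the third record is counted regardless of precedence.

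The result assumes a literal reading, a new record at each change of grade and, for the four relapse chains, links between adjacent records only. Calling those four misclassified also requires reading "present prior to receiving the first dose of study drug or placebo and subsequently worsened" against the pre-dose grade, which is the natural sense but is not spelled out.

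The chain counts describe patterns and say nothing about how often they occur. The direction of any effect between arms is unknown. The possible shift of 5 or 10 points per subject, together with the small cost of repair, makes this worth settling before the tables are programmed.

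**What to change.** Amend the linked-record rule in SAP 3.7.2:

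1. For any linked chain with a pre-dose record, count a post-dose record as treatment-emergent only if its severity exceeds the last pre-dose severity and is worse than that of the immediately preceding record.
2. Apply Case 2 only to chains with no pre-dose record.
3. State that an equal-grade second record is not counted as a worsening. In a wholly post-dose chain the first record still counts.

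Under rule 1 the 5 chains that never exceed the pre-dose grade yield no treatment-emergent record, and the other 7 still yield at least one. The second condition in rule 1 is needed: without it, mild–severe–moderate would count the improving moderate record, which Case 2 now excludes.

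The cost is a few lines of SAP text and derivation code, with no new data.

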9.4.2. Non-Serious Adverse Events

The recording of non-serious AEs will begin after the subject signs the informed consent form and will stop at the end of the subject's follow-up period, which is defined as Study Day 127 / Week 19. The Investigator will monitor each subject closely and record all observed or volunteered AEs on the Adverse Event Case Report Form.

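### SAP 3.7.2 can give two opposite answers for an adverse event with a known pre-dose onset and no complete resolution date, and does not say which prevails

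*Combined protocol and SAP*

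**What the plan says.** SAP 3.7.2 contains three statements that bear on an AE with no linked record.

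- **Start-date rule.** "if the AE (start date/time) occurs prior to the subject’s first dosing date/time, then the AE is not treatment-emergent". The resolution date plays no part.
- **Known-date sentence**, in the later paragraph on dates: "if the onset date or resolution date of an AE is prior to the first study treatment date", then "it will be considered to have occurred prior to the study period".
- **Missing-date sentence**, directly after it. It opens "If the onset or resolution date of an AE is a partial date with only month or year available or complete missing, then the event" and places such an AE, by assumption, inside the study period. The exception is a year before that of first treatment or, in the same year, an earlier month. The sentence does not say whose year and month are meant, the onset's or the resolution's.

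The date paragraph opens with a statement of aim: "The most conservative approach will be used to determine if the event occurs after the treatment". It does not rank the sentences that follow.

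Two protocol sections show that the record in question can occur. Under Protocol 9.4.2, "The recording of non-serious AEs will begin after the subject signs the informed consent form". Protocol 9.4.3.5 provides an outcome for a non-serious AE that never resolves on study: "Patient terminates from the trial and the AE continues".

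**The concern.** The missing-date sentence is triggered by either date. An unknown onset is a good reason to assume, cautiously, that an event followed dosing. An unknown resolution is not: it says nothing about whether a fully dated onset came before dosing. Yet the wording treats the two alike.

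The records exposed are those that a treatment-emergent definition is meant to screen out. AEs are recorded from consent, and screening opens at Day -42 (Protocol Appendix A). Subjects on two antihypertensives stop both for the two-week washout (Protocol 5.1, criterion 9, and 6.1.3). An event that begins in that time and persists is plausible. Incidence and severity of treatment-emergent AEs is the stated safety endpoint (SAP 1.3.3), so two programmers following the same text could produce different safety tables.

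**Working it through.** The plan states no figure on this point to reproduce. The check applies each written rule to sample records.

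**Assumed input.** First dose on 20 June 2019, no linked record. The exception is read two ways: on the onset date and on the resolution date.

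| Record | Known-date sentence | Missing-date sentence, exception on onset | Missing-date sentence, exception on resolution | Start-date rule |
|---|---|---|---|---|
| A. Onset 5 June, ongoing | prior | within | within | not emergent |
| B. Onset 12 May, ongoing | prior | prior | within | not emergent |
| C. Onset 5 June, resolved June 2019, day unknown | prior | within | within | not emergent |
| D. Onset 3 July, ongoing | not triggered | within | within | emergent |

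- **A and C:** the onset month equals the dosing month, so the exception cannot apply on either reading. The missing-date sentence contradicts the other two statements.
- **B:** May precedes June. If the exception looks at the onset, all three statements agree. If it looks at the missing resolution date, there is no month to compare, the exception never operates, and the contradiction returns. An onset in the previous calendar year behaves the same way.
- **D:** no contradiction.

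**How much pre-dose time the unavoidable conflict covers.** Assume that first dose is equally likely on each day of a 30-day month. A first dose on day d leaves d − 1 earlier days in that month.

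- Full pre-dose window of up to 42 days: mean = (0 + 1 + … + 29)/30 = 14.5 days, and 14.5/42 = 35%. Running the actual 2019 calendar also gives 35%.
- Washout of 14 days: mean of min(d − 1, 14) = (105 + 15 × 14)/30 = 10.5 days, and 10.5/14 = 75%.

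So the unavoidable conflict covers about a third of the longest pre-dose window, but most of the washout.

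**Effect of one subject.** About 30 subjects at 2:1 gives 30 × 2/3 = 20 active and 30 × 1/3 = 10 placebo. One reclassified subject moves an incidence by 1/20 = 5 points or 1/10 = 10 points, provided that the subject has no other event in that table row.

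**After correction.** If the assumption applies only when the onset itself is partial or missing, A, B and C are all not emergent and D stays emergent. The statements then agree.

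**The case against.** The strongest reply is that the SAP already gets this right. Its general definition counts an event present before dosing only if it later worsens. The start-date rule and the known-date sentence agree. A programmer who applies either of these first reaches the correct answer. This stands in part: a reader might infer that any AE without a resolution date is classed as occurring after treatment, and the documents do not support that. The inference overlooks both the exception and the sentence just before the rule. What remains is that one written sentence says the opposite, with no ranking. The aim of being conservative could fairly be taken, in safety tables, as a reason to count the event.

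A second reply is that an ongoing event is not the same as one with a missing date. The SAP does not settle this. However, SAP 3.7.2.1 expects injection-site events with a known onset and no resolution date, and record C shows that a merely partial date raises the same conflict.

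A third is that the study period might run from consent, which would make the assumption harmless. The known-date sentence rules this out, since it places everything before first treatment outside the study period.

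A fourth concerns consequence. AE summaries are descriptive with no between-arm test, non-emergent events are flagged in the listing, and onset before dosing should not differ by arm. A pre-dose event would also rarely qualify as related, unless its causality is missing. These points stand and keep the matter minor. One limit is that whether a pre-dose event stays ongoing is settled after dosing, so equal effect on both arms is likely but not assured.

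A reader might also try to estimate the inflation. Assume equal daily AE rates before dosing and over the 127 days from Day 1, with 30% of pre-dose events ongoing at the end. Using all 42 pre-dose days gives 42/127 × 0.3 = 9.9%; using same-month days only gives 14.5/127 × 0.3 = 3.4%. Neither is an estimate for this trial: the rates and the ongoing fraction are not in the documents, and both figures suppose that the missing-date sentence overrides the other two.

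**Conclusion.** Wrong as written (minor). The two date sentences in SAP 3.7.2 contradict each other for an AE with a complete pre-dose onset and a missing or partial resolution date, and neither is given precedence. The contradiction is certain for onsets in the calendar month of first dose. For earlier onsets it depends on reading the exception on the resolution date. Such events could be miscounted as treatment-emergent; the SAP does not clearly class them so. The number affected cannot be computed from the documents. The 35% and 75% shares describe exposed calendar time under the assumed spread of dosing dates, not counts of events. The conclusion treats an ongoing AE as one whose resolution date is missing; for partial resolution dates it does not need that assumption. The primary angiotensinogen analysis is unaffected.

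**What to change.** Replace the missing-date sentence with three statements:

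1. When the onset date is complete, treatment emergence is decided by the onset date and time, together with the existing worsening rule for linked records.
2. Only when the onset date is partial or missing is the event assumed to start on or after first dose, unless the known part of the onset date, or the resolution date (complete, or its known year or month), shows that it was before first dose.
3. A missing or partial resolution date alone never makes an event treatment-emergent.

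The cost is a short SAP edit and a small change to the derivation code. Events whose onset is truly unknown are still handled cautiously, and events with a post-dose onset are unchanged, so the downside is negligible.
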